Negative hematological adaptations due to prolonged periods of strenuous physical activity may, in part, contribute to declines in physical performance during military operations. Exogenous erythropoietin (EPO) is a potential intervention that may be used to maintain hemoglobin (hgb), hematocrit (Hct), and physical performance during periods of high physical activity. The objective of the current study is to determine the ability of EPO to maintain hgb, Hct, and physical performance compared to baseline measures. Additionally, EPO may result in non-hematological adaptations which increase mitochondria biogenesis and alter substrate oxidation. As such, this study will also assess the influence of EPO on whole-body and skeletal muscle substrate oxidation. Eight healthy physically active individuals will be recruited to participate in this longitudinal trial. After exercise practice sessions, volunteers will complete baseline physical performance (time trial) and substrate oxidation testing. Participants will then receive EPO injections 3 times per week for 4 weeks. Diet and exercise will be controlled during the injection period. Participants will undergo four weeks of an intense physical training exercise program. Every seventh day during the injection period a safety blood sample, assessing hematocrit, will be drawn, and participants will complete a 5 km time trial to determine the time course of changes in physical performance can be detected. After the 4 weeks of EPO injections volunteers will complete the same physical performance and substrate oxidation testing. Substrate oxidation will be assessed during 90-min steady-state load carriage (30% body mass) exercise on a treadmill at $55 \pm 5\%$ of $\text{VO}_{2\text{peak}}$. 6-6-[²H₂] glucose tracer technique and indirect calorimetry will be used measure substrate oxidation. Muscle biopsies will be performed to measure muscle glycogen, enzyme activity, and molecular markers of metabolism and inflammation before, and immediately and 3-hrs post exercise. Multiple blood samples will be collected throughout the study to determine alterations in hemoglobin, hematocrit, and markers of substrate metabolism, and inflammation. All study procedures will occur at USARIEM. The primary risks associated with this study include those associated with EPO injection, exercise, blood draws, and muscle biopsies.

B2. BACKGROUND AND SIGNIFICANCE

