adaptations due to reduced iron efflux during overtraining to aid in the maintenance of physical performance has not been explored.

B3. MILITARY RELEVANCE

This study supports the Military Operational Medicine Research Program's Physiological Health and Performance Program Area under the BPE Work Unit. The BPE Work Unit is intent is to execute basic and applied research aimed at identifying and develop biomedical strategies and solutions that safely and ethically enhance Warfighter physical, cognitive, sensory and behavioral performance in training and operational environments, enabling lethality and overmatch. The proposed work aligns to the Physiological Health and Performance Strategic Plan Technical Challenge 1.1.1.1: Identify pharmacological enhancement protocols improving specific task performance under operational stress.

B4. OBJECTIVES/SPECIFIC AIMS/RESEARCH QUESTIONS

Objective

1. Determine the effects of EPO on hematological adaptions compared to baseline during 4 weeks of overtraining.
2. Determine the time course change in physical performance (time trial) with EPO compared to baseline.
3. Assess the influence of EPO non-hematological adaptation (whole-body and skeletal muscle substrate oxidation and glucose turnover) following 4 weeks of overtraining compared to baseline.

Hypothesis

1. Hemoglobin and hematocrit will be maintained with EPO during 4 weeks of overtraining.
2. Physical performance will be maintained with EPO during 4 weeks of overtraining.
3. EPO will increase whole body and skeletal muscle fat oxidation, and reduce reliance on endogenous glucose store following 4 weeks of physical training.

B5. RESEARCH PLAN

B5.1 Research Design

This study will be a longitudinal trial.

B5.2 Research Subjects/Population(s)

B5.2.1 Subject Population(s)

Subject population will be military or civilians representative of active duty male and female service members, being in good health and recreationally active.

B5.2.2 Number of Subjects, Records, and/or Specimens

A total of 8 volunteers will be required to achieve sufficient statistical power. To complete testing on 8 volunteers, we estimate we will need to enroll 60 individuals. All screening will stop once complete data has been collected on 8 volunteers. Records and specimen collection are described in the Research Procedures and Data Collection sections. During briefings and consenting potential participants will be informed that even though they may be eligible and want

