Study Design Overview: Healthy physically active individuals will be recruited to participate in this longitudinal trial. After baseline assessments of body composition, resting metabolic rate (RMR), $\text{VO}_{2\text{peak}}$ and exercise familiarization; volunteers will complete physical performance and substrate oxidation testing (Figure 3). Physical performance will be assessed using time trial. Substrate oxidation will be assessed by volunteers performing 90-min of steady-state load carriage (30% body mass) exercise on a treadmill at $55 \pm 5\%$ of their $\text{VO}_{2\text{peak}}$. 6-6-[$^2\text{H}_2$] glucose will be used as a tracer to assess glucose turnover. Indirect calorimetry will be used to determine carbohydrate and fat oxidation. Muscle biopsies will be performed to measure muscle glycogen, enzyme activity, and molecular markers of substrate metabolism before, immediately after, and 3-hrs post exercise. Multiple blood samples will be collected on substrate oxidation protocol days. To minimize carry over effects of muscle biopsies on subsequent exercise performance, volunteers will not exercise for 3 days. During the first two days of this period, volunteers will undergo carbon monoxide (CO) rebreathing to measure Hgb mass and blood volume. Volunteers will then receive EPO injections 3 times a week for 4 weeks. During the injection period all volunteers will have safety blood draws to assess Hct once a week. Volunteers will also complete a physical performance test once a week to determine time course change in performance with EPO compared to baseline. Exercise training will be controlled during the injection phase, consisting of a combination of endurance- and resistance-type exercise. During the final week of the injection phase body composition, resting metabolic rate (RMR) and $\text{VO}_{2\text{peak}}$ will be reassessed. At the end of the 4-week injection phase volunteers will complete a final physical performance test and substrate oxidation protocol, followed by two CO rebreathing tests on subsequent days. All food and beverages (except water) will be provided to volunteers beginning at the pre injection physical performance and substrate oxidation through the duration of the study. All data collection will occur at USARIEM.

Figure 3: Study Timeline

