movement once the hood is placed over their heads to collect expired air. The test will be discontinued when 20-min of steady state oxygen consumption ($\dot{V}O_2$) and carbon dioxide production ($\dot{V}CO_2$) are recorded. This measurement will be repeated during the last week of the injection phase to assess for changes in RMR. Baseline assessment of RMR, a factor of daily living, and Harris Benedict equation will be used to determine energy needs for study diets.

Study Diets (non-credentialed procedure): Registered Dietitians will develop individualized daily menus using Food Processor SQL (ESHA Research, Salem, OR, Version 10.14). The diets will be derived primarily from components of the US military Meals Ready-to-Eat (MRE) rations to achieve appropriate macronutrient proportions. Energy content of diets during glycogen normalization will match volunteers estimated energy needs to maintain body weight. Volunteers will be consuming a diet providing approximately 55% carbohydrate, 15% protein, and 30% fat. Dietary iron will be controlled for providing a minimum of 18mg/day to ensure recommended dietary allowance (RDA) for both males (8mg/day) and females (18mg/day) is met.

Time Trial (credentialed procedure): Following a 10 hr overnight fast, volunteers will complete a 5 kilometer time trial. The treadmill will be set at a constant 1% grade (36) for the entire test. Following a warm-up period, volunteers will blindly modulate treadmill speed in order to complete the distance as quickly as possible. The only feedback given will be distance covered at half mile increments. At half mile increments volunteers' rate of perceived exertion will be determined using the Borg Scale. Heart rate will be monitored throughout the time trial. Heart rate will be recorded at half mile increments. No motivation will be provided during the time trial. Participants may consume water *ad libitum* during the time trial. Following completion of the test, a self-selected cool-down will occur. Volunteers will complete a minimum of two practice exercise sessions to ensure they are familiar with the performance test. The practice sessions also will establish the coefficient of variation. Study personnel conducting maximal aerobic testing will be credentialed and listed on the DOA log with code "J."

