Study Exercise (non-credentialed procedure): During the injection phase volunteers will conduct prescribed exercise training 4 days and 1 day of physical performance testing (time trial) per week. Volunteers will perform both weighted (treadmill or outdoor; walking, running, and load carriage) and unweighted (cycle ergometry) endurance-type exercise, and resistance-type exercise throughout the protocol. Exercise will be metabolically matched between groups, with exercise-induced energy expenditure being 1000-1500 kcal per day. Prescribed endurance-type exercise will be low-to-high intensity (30-85% $\dot{V}O_2$ peak) using the ACSM metabolic equations for steady-state exercise (37) and the compendium of metabolic equivalents for physical activities. This level of training is similar to that conducted during arduous military training in garrison (38). $\dot{V}O_2$ peak will be assessed after 2 weeks into the injection phase. Exercise intensity will be adjusted based on alterations in $\dot{V}O_2$ peak. Study personnel conducting exercise will be listed on the DOA log with code "V."

Load Carriage Exercise (non-credentialed procedure): Volunteers will complete 90-min of weighted steady-state exercise on a treadmill at $55 \pm 5\%$ of their $\dot{V}O_2$ peak, with 30% of volunteer's body mass. The speed and grade of the treadmill will be determined using the ACSM metabolic equation for walking based on desired $\dot{V}O_2$ (39). Prior to the protocol day, participants will perform a practice session of the treadmill exercise to confirm the prescribed speed and grade are appropriate to induce target $\dot{V}O_2$. The treadmill speed and grade will be maintained for both arms of the study to match the absolute workload of the exercise across treatments. Study personnel conducting treadmill load carriage will be listed on the DOA log with code "V."

Carbohydrate Tracer Study (credentialed procedure): Following an overnight (10 hour) fast, two catheters will be placed into the lower arm (one in each arm). One arm will be used for infusion of 6,6-[2 H₂] glucose tracer and the other will be used for blood sampling. Following an initial blood sample collection to determine background enrichments, a primed, continuous infusion of 6,6-[2 H₂] glucose will begin (prime, 82.2 $\mu\text{mol}\cdot\text{kg}^{-1}$; continuous rate, 0.78 $\mu\text{mol}\cdot\text{kg}^{-1}\cdot\text{min}^{-1}$, **Figure 4**). The 6,6-[2 H₂] glucose will

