5.7.1.1 FDA-approved device being used in this research according to the approved labeling

DEXA, DPX-IQ, Lunar Corporation, True Max 2400, Parvomedics, Sandy, Utah, USA, Polar Electro Inc, Oulu, Finland

5.7.1.2 FDA-approved device being used in this research in a manner other than its approved labeling: N/A

B5.7.2 Drugs

B5.7.2.1 FDA-approved and used in accordance with the approved labeling

B5.7.2.2 FDA-approved and used in a manner not in accordance with its approved labeling:
PROCRIT, EPOETIN ALFA, Janssen Products, LP, Titusville, NJ, USA

B5.7.2.3 Any drug not approved by the FDA: N/A

B5.8 Statistical Analysis

B5.8.1 Sample Size Estimation

Based on results for multiple outcomes across different studies (**Table 4**) a sample size of 8 is required to statistical significance.

Table 4: Previous study effect sizes

Study	Outcome	Delta	Effect Size	Sample Size
Thomson et al. (18)	TTE	10 ± 6	1.40	7
Plenge et al. (24)	Hct	5.1 ± 3	1.56	7
Caillaud et al. (19)	CHO Oxidation	0.7 ± 0.3	1.24	4
Caillaud et al. (19)	Fat Oxidation	0.2 ± 0.05	3.51	2

B5.8.2 Data analysis

Statistical analyses will be conducted using either SPSS (IBM Corp. Armonk, NY), SAS 9.3 (SAS Institute Inc., Carey, NC), or equivalent. Common descriptive statistics will be used to describe volunteer characteristics. Shapiro-Wilk tests will be used to determine normality of data. Paired t-tests will be used to assess phase effects (PRE vs. POST injection) for glucose turnover, and substrate oxidation. Repeated measures ANOVA will be used to assess main effects of time for physical performance. Mixed-model repeated measure ANOVA will be used to assess main effects of phase (PRE vs. POST injection), time and their interaction for blood analytes and muscle molecular analysis. If interactions are significant, appropriate post-hoc correction will be used to examine these relationships. Correlation coefficients and multiple regression analysis will be used to evaluate relationships between study outcome measures. The alpha level will be adjusted for multiple comparisons, with the level for statistical significance set at $P < 0.05$.

SECTION C: HUMAN RESEARCH PROTECTIONS

C1. RECRUITMENT AND CONSENT

C1.1 Identification and Selection of Subjects

Volunteers will be recruited from the federally and non-federally employed civilian population, the Natick Human Research Volunteer (HRV) Pool, and NSSC active duty military personnel.

C1.2 Recruitment Process

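### Objective 2 asks how 5-km performance changes over time against baseline, but the plan specifies only an omnibus time effect and no criterion for 'maintained'

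*Protocol*

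**What the plan says.** **The question.** B4, Objective 2: "Determine the time course change in physical performance (time trial) with EPO compared to baseline". B4, Hypothesis 2: "Physical performance will be maintained with EPO during 4 weeks of overtraining".

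**The measurements.** The opening summary places a time trial before injections ("volunteers will complete baseline physical performance (time trial) and substrate oxidation testing") and one every seventh day during them: "participants will complete a 5 km time trial to determine the time course of changes in physical performance can be detected". B5.3, Study Design Overview, gives the same purpose: "Volunteers will also complete a physical performance test once a week to determine time course change in performance with EPO compared to baseline". B5.3, Time Trial, fixes the test: "volunteers will complete a 5 kilometer time trial". B5.3, Study Exercise, schedules "1 day of physical performance testing (time trial) per week". The Overview also lists a final performance test after the four weeks, without saying whether it is the week-4 trial or an additional one.

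**The analysis.** B5.8.2 and the SAP carry the same sentence: "Repeated measures ANOVA will be used to assess main effects of time for physical performance". A later sentence provides post-hoc correction where an interaction is significant. The last sentence says alpha will be adjusted for multiple comparisons at 0.05, without naming a comparison, reference visit, family or method.

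**The label.** The performance row of the B5.4 table reads 'TTE', as do the performance rows of protocol Table 4 and SAP Table 1 (10 ± 6, effect size 1.40, n = 7). The text does not expand 'TTE', and the abbreviation list in Section E omits it.

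**The concern.** Objective 2 has three parts: which trial, compared with baseline, and in which direction. An omnibus F answers none of them. It tests whether all the trial means are equal, and a significant result is compatible with any pattern of inequality. If the plan is followed as written, the choice of comparisons and of correction is made after the data are seen.

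Hypothesis 2 is harder to serve. It predicts little or no change, so its support has to come from an estimate precise enough to exclude a relevant loss. The plan names neither an estimate nor a criterion. With eight volunteers, a non-significant F may reflect low precision as easily as stable performance.

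**Working it through.** **1. Can the stated post-hoc rule reach performance?** All volunteers receive EPO, and B5.1 describes one longitudinal trial. The performance model has one within-subject factor, time. The phase-by-time model, which does have an interaction, is assigned to blood analytes and muscle. The trigger therefore cannot occur for performance.

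**2. The plan's own figure.** Exact paired t-test, two-sided 0.05, power assumed to be 80% because no value is stated, effect size 1.40: power is 78.1% at n = 6, 86.7% at n = 7 and 92.2% at n = 8. The tabulated n = 7 reproduces. It covers a single before-after contrast on 'TTE', not a time course of 5-km time.

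**3. How often F misses a true 2% change.**
- Inputs: n = 8 (B5.8.1) and five trials, namely baseline plus four weekly.
- Assumptions: the 2% change, the CV, and independent errors of equal size at each trial. B5.3, Time Trial, says only that practice sessions will establish the CV.
- Formula: noncentrality λ = n × Σ(mean of trial − overall mean)² / CV², with F on 4 and 28 degrees of freedom and critical value 2.714.
- Steady change (0, 0.5, 1, 1.5, 2): the sum of squares is 2.5, so λ = 20/CV².
- Last trial only (0, 0, 0, 0, 2), or a step at week 1 (0, 2, 2, 2, 2): the sum of squares is 3.2, so λ = 25.6/CV².

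| CV | F non-significant, steady | F non-significant, last only or step |
|---|---|---|
| 1% | 7.3% | 2.5% |
| 1.5% | 43% | 30% |
| 2% | 66% | 57% |
| 3% | 84% | 80% |

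Simulation (40,000 studies per scenario, CV 1.5% to 3%) agrees to within about one percentage point. With six trials and CV 2%, simulated power is 35% (steady), 42% (last only) and 41% (step), so F misses in 65%, 58% and 59%. The result does not depend on the trial count.

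**4. A significant F need not mean a change by the end.** Suppose week 1 is at +1.5%, week 3 at −1.5%, and the other trials, including the final one, equal baseline. At CV 2%, λ = 8 × 4.5/4 = 9 and F is significant in 58% of studies.

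**5. What a paired interval gives.** The half-width is t(0.975; 7)/√8 = 2.365/2.828 = 0.836 SD of the change. If that SD is CV × √2, the half-width is 1.18 × CV: ±1.2%, ±1.8%, ±2.4% and ±3.5% at CV 1%, 1.5%, 2% and 3%. The change detectable with 80% power, two-sided 0.05, is 1.156 SD. At CV 2% that is 1.156 × 2 × √2 = 3.3%, with a range of 2.5% to 4.9% for CV 1.5% to 3%.

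**6. Weekly contrasts against the omnibus test.** Simulated power at CV 2% with a 2% change, Holm over all four post-baseline contrasts:

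| Pattern | Holm, any week | Omnibus F | Final vs baseline, paired, unadjusted |
|---|---|---|---|
| Steady | 27% | 34% | 41% |
| Last only | 20% | 43% | 41% |
| Step | 45% | 43% | 41% |

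When the mean change is zero but individual changes vary with SD 2%, Dunnett contrasts with pooled error give family-wise error of 6.0%, 4.8% and 8.0% for the three patterns. Holm on paired differences gives 4.4%, 4.7% and 4.2%. This favours paired differences.

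**The case against.** **The alpha sentence implies follow-up comparisons.** This stands in part. The plan does not forbid them, so it would be wrong to say that week-by-week results are impossible under it. What can be said is that none is specified. Baseline-only, all-pairwise and final-only comparisons would all comply.

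**Nothing says a non-significant F will be read as maintenance.** Correct. A reader might infer that intention from Hypothesis 2 beside the ANOVA, but the documents do not state it. The supportable criticism is that no criterion is given.

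**The percentages rest on assumed values.** Also correct, and they move greatly: at CV 1% the F-test rarely misses a 2% change. They illustrate the point and do not carry it. The specification gap exists at any CV.

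**The trial count is uncertain.** It is, and the timeline figure is not available here, so it may be settled there. The conclusion holds for five or six trials.

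**'TTE' may be harmless.** A reader might infer that it means time to exhaustion and that the study was sized on a different endpoint. The documents do not show that. The label is undefined, Section E points to an outside guide, and Table 4 presents effect sizes from earlier studies without claiming power for 5-km time. It is a label to reconcile, not a demonstrated conflict.

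**There may be a second group.** B5.3 refers to groups and arms under the exercise procedures, but no comparison group is defined anywhere and the performance analysis names only time.

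**Conclusion.** The point holds as a gap between objective and analysis. The specified test does not identify which trial differs from baseline or in which direction, the post-hoc rule cannot apply to it, and no result is named that would support Hypothesis 2. With n = 8, a non-significant F would not establish maintenance. At an assumed CV of 2% it would accompany a true 2% change in 57% to 66% of studies; over CV 1% to 3% the range is about 2.5% to 84%. These figures assume five trials, independent equal errors and the three patterns shown.

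No general gain in power is claimed for named contrasts. The gain is an answer by week, with direction and interval, fixed before the data are seen. The matter should be corrected; it does not call for new data or more volunteers.

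**What to change.** In B5.8.2 and the SAP:

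1. State how many post-baseline 5-km trials there are, and whether the final test is the week-4 trial or an extra one.
2. Make the mean paired difference, final minus pre-injection baseline, with its unadjusted 95% confidence interval, the single deciding result for Hypothesis 2. Judge maintenance from that interval, against a margin if the sponsor states one, and not from non-significance. Say that this contrast stands outside the adjusted family, so that the alpha sentence is consistent with it.
3. For the time course, pre-specify each earlier weekly trial against baseline as paired differences with Holm adjustment, not conditional on the omnibus F or on an interaction. Report mean differences with Bonferroni-adjusted intervals as descriptive, and note that Holm tests and Bonferroni intervals can occasionally disagree. Keep the omnibus F as an overall test.
4. Define 'TTE' in B5.4, Table 4 and SAP Table 1, or reconcile it with the 5-km trial. Unless it is shown to be that trial, do not cite its row as power support for 5-km time. State instead that n = 8 detects a paired change of about 1.16 SD of the change at 80% power, two-sided 0.05.

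**Cost.** Wording only; same data, same volunteers. Adjusted weekly contrasts can be less powerful than the F-test for some patterns. With Holm over all four contrasts and only the last trial moving at CV 2%, power is about 20% against 43%. Keeping the final contrast separate avoids that loss for the final trial (41%), but the final test and the weekly family are then each held at 0.05, so their joint error is bounded by 0.05 + 0.05 = 0.10. The Bonferroni intervals are wide. At CV 2% the half-width is 3.128/√8 × 2 × √2 = 3.1% for three earlier trials, and 3.335/√8 × 2 × √2 = 3.3% for four.
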